Primary objective

To identify clinical predictors of myocardial injury in patients hospitalized for COVID-19 infection since the introduction of vaccines (i.e., March 1, 2021).

Secondary objectives

1. To evaluate if the presence of myocardial injury during the index hospitalization for COVID-19 is associated with a worse in-hospital clinical course in terms of in-hospital complications and need for aggressive therapies.
2. To evaluate if the presence of myocardial injury during the index hospitalization for COVID-19 are associated with a worse angina status and quality of life (evaluated using the Seattle Angina Questionnaire [SAQ] summary score (15)) at 12-months follow-up.
3. To evaluate if the presence of myocardial injury during the index hospitalization for COVID-19 predicts a worse clinical outcome in terms of major adverse cardiovascular events (MACE) (defined as the composite of cardiovascular death, ischemic heart disease [acute or chronic coronary syndromes], stroke/transient ischemic attack [TIA] and hospitalization for heart failure), dysrhythmias (defined as the composite of new-onset atrial fibrillation and/or ventricular arrhythmias), inflammatory heart disease (pericarditis and/or myocarditis) or thrombotic disorders (pulmonary embolism, deep vein or superficial vein thrombosis) at 12-months follow-up.

METHODS

Study design

Retrospective and prospective observational study.

Population

All consecutive patients hospitalized at Policlinico Universitario A. Gemelli IRCSS since March 1, 2021, with a diagnosis of SARS-CoV-2 infection (≥ 1 positive nasopharyngeal swab) and at least one value of high-sensitivity cardiac troponin I (hs-cTnI) measured during the index hospitalization will be enrolled. Given that the patients are unable to physically sign the informed consent form due to epidemiological reasons (contamination of papers by SARS-CoV-2), each patient will verbally declare the consent to “Consenso al trattamento dei dati personali e dei campioni biologici a scopo di ricerca – no profit”, “modulo di dichiarazione della volontà espresso ai fini del consenso informato generale alle cure” and “modulo dossier sanitario – richiesta di oscuramento/deoscuramento di eventi/episodi” at the presence of at least two witnesses.

Inclusion criteria

- Age ≥ 18 years;
- Overt COVID-19 infection (molecular nasopharyngeal swab positive for SARS-CoV-2 ≥ 1);

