- Patient with at least a high sensitivity Troponin I measured during hospitalization course.
- Available data on vaccination.
- Verbal informed consent

Exclusion criteria

- Age <18 years;
- Patient in whom at least one high sensitivity Troponin I value measured during the course of hospitalization is not available.
- No data available on vaccination status.

Variables and procedures

This study will make use of Data Mart COVID-19 developed within Generator Real World Data Unit. The Data Mart COVID-19 belongs to the family of the diagnostic and prognostic mini-bots developed within the Generator Real World Data Unit project in which artificial intelligence solutions (such as text mining) are adopted to automatically extract both structured and unstructured data from hospital databases of patients infected from SARS-CoV-2. Feature selection and machine learning algorithms can be applied to develop diagnostic and prognostic support systems for clinicians.

The specific data that which will be exploited are:

- Demographics data;
- Patient comorbidities, vital signs and symptoms at the time of admission;
- Laboratory analysis;
- In-hospital complications (e.g.: need for non-invasive or invasive ventilation, access to intensive care unit, length of hospitalization, use of glucocorticoids or antibiotics, death);

- Blood gas exchange information;
- Radiological reports;
- Medications at the time of admission, during hospitalization and at the time of discharge;
- Vaccination status.

Clinical follow-up

All patients will undergo a clinical follow-up by telephonic interview and/or clinical visit at 12 months from hospital discharge, during which the incidence of MACE, dysrhythmias, inflammatory heart disease and/or thrombotic disorders (both as incidence of the composite and as incidence of each individual components) in the past months will be investigated, the SAQ will be administered and the SAQ summary score will be collected.

ENDPOINTS

Primary endpoint

To assess for the presence of clinical predictors for the occurrence of myocardial injury, defined as at least one value of hs-cTnI >99th percentile upper reference limit (16), in patients hospitalized for COVID-19 infection.

Secondary endpoints

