1. The occurrence of myocardial injury during the index hospitalization for COVID-19 infection will be correlated with in-hospital complications (defined as the composite of the need for non-invasive or invasive ventilation, access to intensive care unit, length of hospitalization, use of glucocorticoids or antibiotics, and death).
2. The occurrence of myocardial injury in patients during the index hospitalization for COVID-19 infection will be included in a prediction model and correlated with future cardiovascular events (MACE), dysrhythmias, inflammatory heart disease and/or thrombotic disorders at 12-months follow-up.
3. The occurrence of myocardial injury during the index hospitalization for COVID-19 infection will be correlated with angina status and quality of life, evaluated using the SAQ summary score, at 12-months follow-up.

STATISTICAL ANALYSIS PLAN

Sample size calculation

A comprehensive characterization of myocardial injury in COVID-19 infection is still lacking, and no clinical predictors of myocardial injury has been identified yet. Moreover, the long-term cardiovascular outcome of myocardial injury in the post-acute COVID-19 phase is largely unknown. Thus, this configures as a pilot study on large-scale cohort. As such no formal sample size calculation is needed. However, based on the COVID-19 datamart of our clinical institution and on inclusion criteria, we expect to include in the study around 2000 patients hospitalized with COVID-19. Such a sample size is largely consistent with common rules of thumb for pilot studies. In addition, the estimated sample size is largely consistent with the van Smeden metamodels related to the new statistical approaches for the development of clinical prediction models (17). The square root of the mean squared prediction error (rMPSE) and mean absolute prediction error (MAPE) may be approximated via the results of these. Lower values for rMSPE and MAPE indicate better performance. For instance, at a sample size of $N=400$, with $P=8$ candidate predictors and an expected event fraction of $\frac{1}{4}$, the predicted out-of-sample rMPSE would be 0.065 when ML model (without variable selection) is applied, and 0.053 for Ridge regression; MAPE would instead be 0.045 for the ML model and 0.038 for the Ridge regression.

Statistical analysis

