All demographic, clinical and laboratory characteristics will be summarized by descriptive statistics techniques. In depth, qualitative variables will be expressed by absolute and relative percentage frequencies. Quantitative variables, indeed, will be reported either as mean and standard deviation (SD) or median and interquartile range (IQR), respectively in the case they were normally or not normally distributed. Their distribution will be previously assessed by the Shapiro Wilk test. Between groups differences in the demographic, clinical, laboratory and pathologic features will be assessed by the Chi Square or the Fisher's exact test as for qualitative variables, with Yates correction, as appropriate, whilst quantitative variables will be evaluated either by the Student's t test or the Mann-Whitney U test, according to their distribution. Univariable and multivariable logistic regression models will be performed to evaluate the presence of clinical predictors for the occurrence of myocardial injury in COVID-19 infection. Results will be expressed as odds ratio (OR) with 95% confidence interval (CI). Model calibration performances will be evaluated via the Hosmer-Lemeshow goodness of fit test with 10 groups. Model performance will be assessed through receiver-operator characteristic (ROC) curve analysis by reporting the area under the curve, sensitivity, specificity and +/- likelihood ratio (LR). Univariable and multivariable logistic regression analysis will be performed also to assess the association of myocardial injury in COVID-19 infection with in-hospital complications and need for aggressive therapies.

Univariable and multivariable multiple linear regression will be instead used to assess

whether SAQ summary score at 12-months follow-up is affected by myocardial injury in patients with COVID-19 infection.

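### The in-hospital composite counts any glucocorticoid or antibiotic use as equal to ventilation, ICU access or death, so it can dilute or create an association read as a worse clinical course

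*Protocol*

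**What the plan says.** The protocol's Secondary endpoints, item 1, describes in-hospital complications as "defined as the composite of the need for non-invasive or invasive ventilation, access to intensive care unit", followed by length of stay, "use of glucocorticoids or antibiotics, and death". Variables and procedures repeats the list ("length of hospitalization, use of glucocorticoids or antibiotics, death"), again without saying which drug use counts.

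Secondary objectives, item 1, sets the aim as a "worse in-hospital clinical course in terms of in-hospital complications and need for aggressive therapies". The hypotheses that close the introduction speak of escalation of therapies.

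The Statistical analysis section fixes the model: "Univariable and multivariable logistic regression analysis will be performed also to assess the association of myocardial injury in COVID-19 infection with in-hospital complications" and with the need for aggressive therapies. Results for the individual components are promised for the 12-month events (Clinical follow-up and the Cox regression paragraph). No such statement is made for the in-hospital composite.

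**The concern.** Logistic regression needs a yes/no outcome. Read literally, a patient scores yes on any one listed item, so a single course of an antibiotic or glucocorticoid weighs as much as invasive ventilation or death. There is no condition on indication, duration, new start or escalation.

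Two errors can follow. If drug use is common and similar in patients with and without injury, it adds positives to both groups and hides a real difference in severe outcomes. If drug use differs between the groups for other reasons, the composite shows an association although ventilation, ICU access and death do not differ. In either case the odds ratio does not answer objective 1. It is also the only in-hospital endpoint defined for that objective.

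**Working it through.** The protocol states no rate, effect size or power for this endpoint, so there is no figure to reproduce. What follows shows how the definition behaves under stated assumptions.

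**Inputs**
- From the protocol: N about 2000 ("we expect to include in the study around 2000 patients hospitalized with COVID-19") and two-sided alpha 0.05.
- Assumed: 25% with myocardial injury, borrowed from the event fraction in the protocol's sample-size illustration, giving 500 against 1500 patients.
- Assumed: s, the rate of ventilation, ICU access or death (severe events), and u, the use of either drug among patients without a severe event.
- Length of stay is left out, because it has no cut-off and cannot be scored yes/no as written.

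**Formulas**
- Composite rate = s + (1 − s)u.
- Drug-only share of positives = 1 − (overall severe rate) / (overall composite rate).
- Power: two-proportion z-test, pooled variance under the null.

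**Dilution, moderate effect.** s = 22% with injury and 15% without; overall severe rate 0.25 × 22% + 0.75 × 15% = 16.75%. Example at u = 40%: 0.22 + 0.78 × 0.40 = 53.2%, against 0.15 + 0.85 × 0.40 = 49.0%.

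| u, both groups | Composite, injury vs none | OR | Power | Drug-only share |
|---|---|---|---|---|
| severe events only | 22.0% vs 15.0% | 1.60 | 94% | – |
| 20% | 37.6% vs 32.0% | 1.28 | 63% | 50% |
| 40% | 53.2% vs 49.0% | 1.18 | 37% | 67% |
| 60% | 68.8% vs 66.0% | 1.14 | 21% | 75% |
| 80% | 84.4% vs 83.0% | 1.11 | 10% | 80% |

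Injury shares of 15% and 40%, and severe rates of 20% vs 10% or 30% vs 20%, show the same pattern.

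**When more than half of patients score positive.** This needs u > (0.5 − s)/(1 − s): 44% for s = 10%, 38% for s = 20%, 29% for s = 30%.

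**Dilution, large effect.** s = 60% vs 30%, OR 3.5, risk difference 30 points, drug use independent of severity and injury:

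| Drug use | Composite | Risk difference | OR | Power |
|---|---|---|---|---|
| 50% | 80% vs 65% | 15 points | 2.15 | >99% |
| 70% | 88% vs 79% | 9 points | 1.95 | >99% |
| 85% | 94% vs 89.5% | 4.5 points | 1.84 | 88% |
| 95% | 98% vs 96.5% | 1.5 points | 1.78 | 37% |

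If instead every severe patient receives one of the drugs, the same overall use leaves less among the others. The overall severe rate is 0.25 × 60% + 0.75 × 30% = 37.5%.
- Overall use of 50% means u = (0.50 − 0.375)/0.625 = 20%: risk difference 24 points, OR 2.70.
- Overall use of 70% means u = (0.70 − 0.375)/0.625 = 52%: risk difference 14.4 points, OR 2.13.

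**Spurious association.** s = 15% in both groups, u = 70% with injury and 60% without: 0.15 + 0.85 × 0.70 = 74.5%, against 0.15 + 0.85 × 0.60 = 66.0%. The OR is 1.51 and power is 95%.

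**The case against.** A reader might infer that these drugs are routine, that most patients will therefore score positive, and that little contrast will remain. The protocol does not support that. It gives no usage rate, and at 20% use most patients would not be positive under any of the severe rates above. With a large true effect (60% vs 30%), power stays at 88% or more up to 85% drug use. Assuming that drug use is independent of severity also overstates the dilution, as the calculation with all severe patients treated shows. This part of the objection stands, and it makes the size conditional.

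A reader might also infer that a steroid continued from home is meant to count. The protocol does not say so. It files drug use under in-hospital complications, its hypothesis is escalation, and it collects "Medications at the time of admission, during hospitalization and at the time of discharge". New or escalated treatment is probably what was intended, but the endpoint does not say that either.

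The term composite may be used loosely, and an analysis plan that is not shown may add component results. That mitigates only in part, because the protocol itself defines the endpoint as the composite. Finally, objective 1 includes therapies, so drug use has a legitimate place in the study. That stands, and it argues for testing drug use separately rather than only describing it. The stakes are limited: this is one secondary endpoint of an observational study that calls itself a pilot.

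**Conclusion.** The concern holds in conditional form, with medium confidence. The wording fault is certain: unqualified drug use sits level with ventilation, ICU access and death in one yes/no outcome, and this does not match the stated aim. How much harm follows depends on rates that the protocol does not give.

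With a moderate effect on severe outcomes the loss is serious even at modest drug use: power is already down to 63% at 20% use, with about half of the positives there for drug use alone. With a large effect the test survives at most usage levels, but the odds ratio still shrinks from 3.5 to about 1.8–2.2 under independence, or to 2.1–2.7 at 50–70% overall use if all severe patients are treated. A difference in prescribing alone can produce a significant result. The documents do not establish that most patients will score positive or that severe outcomes will cease to matter.

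**What to change.** In Secondary endpoints, item 1, restrict the yes/no composite to non-invasive or invasive ventilation, ICU access and death. Analyse glucocorticoid use and antibiotic use, each counted only when newly started during the stay, as separate outcomes for the aggressive-therapies part of objective 1, each with its own logistic odds ratio. Report every component, with length of stay on its own. Make the change before the analysis, so that it cannot look driven by results.

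No new data collection should be needed: the components are already listed for extraction, and medications are recorded both at admission and during the stay, so new starts can be derived. The costs are a lower composite event rate (16.75% in the moderate scenario, against 50% with drug use at 40%) and a few more secondary comparisons. The change concerns what the endpoint counts and implies nothing about treatment.

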Finally, to assess whether the presence of myocardial injury during COVID-19 predicts a worse outcome, in term of both MACEs at 12 months and single components, uni- and multivariable interaction proportional hazard Cox regression models will be computed. We will consider, as for MACEs, time to first event, and for each component, time to each event. To evaluate combined effects between each clinical/laboratory predictor and presence/absence of Myocardial Injury (MI), multivariable interaction Cox models will be fitted, and the interaction hazard ratios (IHR) evaluated. In particular, for each predictor, one interaction Cox model will be fitted. In this framework, IHR = 1 indicates no synergy between predictor and MI, IHR <1 expresses a reduction of hazard due to the synergy, while IHR >1 an increased hazard. The interaction parameters (IHR) will be interpreted as difference (in HR terms) of the predictor and MI (absence of MI as reference category). Proportionality of the hazard functions will be assessed by visual inspection of hazard plots and Schoenfeld residuals. When proportionality was doubtful, weighted Cox regression models would be fitted.

A two-tailed analysis will be performed and a p value <0.05 will be considered as statistically significant. Statistical analyses will be performed using R software version 4.2.1 (CRAN®, R Core 2021) (and its packages *survival*, *survminer*, *coxphw* and *Hmisc*) (18).

Data privacy and data protection

Privacy issues related to this project have been analyzed with Policlinico Gemelli Data Protection Officer (D.P.O.). As a GENERATOR RWD study, this project will be compliant with GDPR Italian and European directives and regulation (EU Directive 2016/679 and under Italian Laws: Decreto Legislativo 196/2003, Decreto Legislativo 101 2018, Autorizzazione Generale Garante 9/2016)

The guidelines for data privacy are covered by two main documents prepared with the D.P.O.:

- Generator main document “Linee Guida Utilizzo Real World Data” which prescribes the governance mechanisms for Generator through two main bodies (Comitato di Supervisione and Comitato Operativo) where representatives appointed from IRCSS and other key Units of Policlinico participate and have mandate to decide;
- “Orizzonte Normativo Real World Data” prepared by the D.P.O., which provides the directives for the execution of any Generator study to assure its compliance with European and Italian GDPR directives.

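### The two-group rule for quantitative variables makes no provision for unequal variances and lets a Shapiro-Wilk test pick the method; if the smaller group is more variable, its error rate rises modestly above 5%.

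*Protocol*

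**What the plan says.** The Statistical analysis section of the protocol sets a two-stage rule. On quantitative variables it first states: "Their distribution will be previously assessed by the Shapiro Wilk test". It then says that "Between groups differences in the demographic, clinical, laboratory and pathologic features will be assessed", and for quantitative variables that "quantitative variables will be evaluated either by the Student's t test or the Mann-Whitney U test, according to their distribution". The same normality check also decides between mean with SD and median with IQR in the descriptive tables.

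The section closes with the level: "A two-tailed analysis will be performed" and "a p value <0.05 will be considered as statistically significant".

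Four things are not stated: which groups are compared, whether Shapiro-Wilk is run on all patients together or within each group, at what level it is judged, and what happens when the variances differ.

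On size, the Sample size calculation section says "we expect to include in the study around 2000 patients hospitalized with COVID-19". An injured share of 1/4 appears only in a worked example at N = 400, with 8 "candidate predictors and an expected event fraction of" 1/4.

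**The concern.** Student's t test, in its usual meaning, pools the two variances. When group sizes differ and the smaller group is the more variable one, the pooled standard error is too small and equal means are declared different too often. Within a group, Shapiro-Wilk looks at shape and cannot see that the other group has a different spread.

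The screen also behaves badly at this size. With about 2000 patients it reacts to skewness that does the t test no harm, so sample size rather than suitability decides which test is used.

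At stake are the unadjusted comparisons of demographic, clinical and laboratory features. They are numerous and each is judged at 0.05, so a raised error rate would add spurious differences to the description of patients with myocardial injury.

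**Working it through.** **Inputs**
- From the protocol: total N of about 2000; two-sided level 0.05; Student's t or Mann-Whitney, selected by Shapiro-Wilk.
- Assumed: the groups are injured versus uninjured (inferred from the objectives); 25% injured, so n1 = 500 and n2 = 1500 (the 1/4 is only the worked example; 10%, 40% and 50% are also shown); Shapiro-Wilk judged at 0.05; SD ratio s (injured to uninjured) from 0.67 to 2, because no SDs are given.

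**Step 1: Student's t alone, large-sample formula**

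With the uninjured SD set to 1:
- true variance of the difference: V_true = s²/n1 + 1/n2
- variance the pooled test uses: V_pooled = s²/n2 + 1/n1
- actual type I error = 2 × [1 − Φ(1.96 × √(V_pooled/V_true))]

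At s = 1 both variances are 1/500 + 1/1500 = 0.002667, which returns the protocol's own 5.0%.

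At s = 1.5: V_true = 2.25/500 + 1/1500 = 0.005167; V_pooled = 2.25/1500 + 1/500 = 0.003500; the ratio is 0.677 and its root 0.823. Then 1.96 × 0.823 = 1.613, and the error is 10.7%.

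The ratio depends on the injured share and s, not on total N. The formula gives the same values at N = 400 and N = 2000, so a larger cohort does not help.

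| Injured share | s = 0.67 | s = 1 | s = 1.25 | s = 1.5 | s = 2 |
|---|---|---|---|---|---|
| 10% | 0.7% | 5.0% | 10.1% | 15.4% | 24.5% |
| 25% | 1.7% | 5.0% | 7.9% | 10.7% | 15.0% |
| 40% | 3.4% | 5.0% | 6.1% | 7.0% | 8.2% |
| 50% | 5.0% | 5.0% | 5.0% | 5.0% | 5.0% |

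**Step 2: the rule the protocol actually describes**

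Simulation at 500 versus 1500: normal data, equal means, 3000 runs per setting. The Monte Carlo standard error at 5% is √(0.05 × 0.95/3000) = 0.4 points. The share of runs passing Shapiro-Wilk, and so reaching Student's t, is in brackets.

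| s | Student alone | Mann-Whitney alone | Gated rule, pooled check | Gated rule, per-group check | Welch |
|---|---|---|---|---|---|
| 0.67 | 1.9% | 3.0% | 2.2% (61%) | 1.9% (90%) | 4.9% |
| 1 | 5.2% | 4.9% | 5.3% (95%) | 5.3% (90%) | 5.0% |
| 1.25 | 7.2% | 5.5% | 6.8% (84%) | 7.2% (90%) | 4.4% |
| 1.5 | 11.0% | 8.0% | 8.4% (14%) | 10.8% (90%) | 4.9% |
| 2 | 15.2% | 10.4% | 10.4% (0%) | 15.1% (89%) | 5.1% |

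Repeat simulations of the gated rule gave similar or slightly lower values. That is why the summary figures are about 7% / 8% / 9–10% (pooled) and 7% / 10–11% / 14–15% (per group).

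At 10% injured and s = 1.25 / 1.5 / 2, the gated rule gives 9.9% / 11.1% / 11.8% (pooled) and 10.0% / 14.2% / 23.3% (per group). At 50% injured it stays between 5.1% and 5.8% at these ratios. Welch at 10% injured lies between 4.5% and 5.0%.

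**Step 3: how the screen behaves at n = 2000**

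Gamma samples with skewness 0.1 / 0.2 / 0.28 are rejected in 37% / 92% / 100% of runs; a repeat gave 34% / 90% / 99.6%. Skewness 0.45, a t distribution with 10 df, and normal values rounded to a fifth of an SD are rejected in 99% to 100%. In the settings with skewness 0.28 or 0.45, 10 df or rounding, with equal variances, Student's t has an error of 4.5% to 5.7%. The screen thus discards the t test where it works.

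**The case against.** The strongest reply is that the two complaints pull against each other. If Shapiro-Wilk rejects trivial skewness at this size, Student's t is seldom run. With a per-group check and skewness 0.28 it is reached in about 1% of runs. A reader might take 7.9% / 10.7% / 15.0% as the error rate of the planned comparisons. The documents do not support that: those figures belong to Student's t applied to every variable without a screen. The planned rule comes close to them only if the check is per group and the data are almost exactly normal. On pooled data the screen does give some protection, because mixing two spreads makes heavy tails that it detects. This stands, and the gated figures are the ones to use. They still exceed 5% at every SD ratio above 1 shown for 25% injured, because Mann-Whitney is also off under unequal spread.

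Second, the inputs are not the protocol's. No SDs are given, the 1/4 is illustrative, and the groups are inferred. This also stands: the size is conditional, and the direction reverses if the smaller group is less variable.

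Third, no objective depends on these tests. For the primary objective, "Univariable and multivariable logistic regression models will be performed to evaluate the presence of clinical predictors for the occurrence of myocardial injury"; in-hospital complications use logistic regression, the SAQ score linear regression and 12-month events Cox models. A reader might infer that false positives here feed into the predictor models, but nothing in the protocol says that these p-values select model variables.

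Fourth, the choice of t-test variant is often left to a separate SAP, and this pairing of tests is conventional. But the protocol names both the tests and the selector, so the rule is fixed here. Being conventional does not make it well suited to unequal groups.

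**Conclusion.** The point holds in a limited, conditional form. The stated rule has no provision for unequal variances, and its normality screen is a poor selector at about 2000 patients. With 25% injured, equal means, near-normal data and an injured SD 1.25 to 2 times larger, the nominal 5% becomes about 7% to 10% (pooled check) or 7% to 15% (per-group check). It is larger at 10% injured, essentially nominal at 50%, and conservative (Student's t 1.7%) at an SD ratio of 0.67.

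What rests on the text is the rule itself, the level and the expected N. The SD ratio, the injured share and the grouping are assumptions. A Mann-Whitney rejection under unequal spread is wrong only if read as a difference in means; the distributions do differ. No primary or secondary conclusion is put in doubt. This is a free improvement to the descriptive comparisons.

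**What to change.** In the Statistical analysis section:

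1. Name Welch's t test, in place of Student's t, for comparing means.
2. Remove Shapiro-Wilk as the selector of tests and summaries. List in advance, by variable, the clearly skewed measures that will be summarised by median and IQR and compared by Mann-Whitney; all others get mean, SD and Welch's test. A list fixed beforehand avoids replacing one data-driven choice with another.
3. State that Mann-Whitney results are read as a difference in distribution, not in means. Welch does not cure that branch, so the interpretation has to be fixed in words.
4. Name the groups being compared.

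The cost is a few lines of wording. When the SDs are equal, the pooled and Welch standard errors estimate the same quantity (V_pooled = V_true at s = 1). The only loss is in degrees of freedom, which is negligible with groups of this size. No new data are needed and the regression models are unaffected.
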